#### Predictors of baseline physical activity

4. Exploratory: We will analyze predictors of baseline physical activity. Baseline variables tested will include age, gender, body mass index (BMI), six minute walk distance, FEV1, self-efficacy (using the PRAISE questionnaire), motivation for exercise (using the BREQ-2 instrument, questionnaire), MRC dyspnea, health status (using the self-administered Chronic Respiratory Disease (CRQ) questionnaire, anxiety and depression (HADS questionnaire, appendix), sleep efficiency and awakenings (from DynaPort output), functional performance using the Timed Up and Go (TUG) test.

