### Sample size estimates

Sample size estimates are based on Langer et al. Am J Transpl 2012 and using <http://www.biomath.info/power/ttest.htm>. Patients following lung transplantation were randomized to exercise training or standard care. Walking activity (min/day) from baseline to 12 weeks increased from  $36 \pm 16$  to  $56 \pm 24$  in the treatment group. Assuming a treatment difference, in minutes, of 18 and a SD of 20 and a within-group analysis, an n of ~ 12 would have a power of 0.80 to show this difference. We expect our improvement in walking time with rehabilitation in COPD patients will be less robust. Assuming an increase in activity (minutes per day of walking) of 10 minutes would require an n of 34 to give a power of 0.80, but an improvement of 8 minutes would require 52 patients. Forty evaluable patients appears to be a reasonable number.

Number of subjects: Our goal will be to recruit 40 patients with evaluable data at 12 weeks. Assuming 10 dropouts during rehabilitation, we would need to recruit 50.

Study period: Recruitment over the 6 sites will be over 10 months (~ 40 weeks). Since study follow-up is for 48 weeks per patient, the study will last approximately 84 weeks from first patient in to last patient out.

Activity measurement: We will use the DynaPort MoveMonitor to assess: sedentary activity, upright activity, walking activity, activity intensity, and steps per day. Activity will be measured for 7 consecutive days, 3 days (12 hours per day) minimum. Patients will be asked to wear the devices 24 hours per day, if possible.

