Responsibilities for SAE reporting: The Investigators shall report (i.e., from signing the informed consent onwards through the trial defined follow-up period) all SAEs and non-serious AEs which are relevant for a reported SAE by fax or other secure method using BI SAE Form to the BI Unique Entry Point in accordance with timeline specified below.

v. Within five (5) calendar days upon receipt of initial and follow-up SAEs containing at least one fatal or immediately life-threatening event;

vi. Within ten (10) calendar days upon receipt of any other initial and follow-up SAEs.

vii. BIPI Unique Entry Point:

Boehringer Ingelheim Pharmaceuticals, Inc.  
[name]  
[contact]  
E-mail: PV\_global\[contact]

For each adverse event, the investigator will provide the onset date, end date, intensity, treatment required, outcome, seriousness, and action taken with the BI marketed drug. The investigator will determine the expectedness of the BI marketed drug to the AEs as defined in the Listed or BI Drug Information e.g. Investigator's Brochure, Summary of Product Characteristics (SmPC) or Product Information (PI).

- d. Physical activity measurements, each over 7 days
  - e. Outcomes testing
  - f. Scripted exercise at home directions (except 48 week visit)
6. Comments: Three to 5 days of activity testing is considered adequate to capture a particular patient's activity profile (ERS Statement on Physical Activity, submitted for publication). We will accept a minimum of three days of activity measurement for each assessment. Twelve hours per 24 hour day of activity assessment will be considered a day's measurement. Although we will ask patients to wear the devices day and night, we anticipate many will not wear them at night because of inconvenience. Therefore, a requirement of 12 of a potential 16 hours (75% wear-time) appears reasonable. The DynaPort device has an algorithm that determines wear time. If a missing observation occurs over the course of the 48-week study (such as from technical problems, two or more exacerbations in that time block, etc.), we will carry the last observation forward into that missing spot.

Safety considerations: Pulmonary rehabilitation will be performed per usual protocol by centers with considerable experience in providing this intervention. The DynaPort device is registered with the FDA:

<http://www.accessdata.fda.gov/scripts/cdrh/cfdocs/cfrl/rl.cfm?rid=145003>

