### Data analysis

The primary variable to be assessed will be changes in daily walking activity (in minutes) from baseline to week 12. The statistical approach for this will be a repeated measures analysis of variance using SAS. Covariates may be added, if necessary. We anticipate day of week variation (Sundays have less activity) and seasonal variation (less activity in winter). This will be handled by including these variables as covariates in the analysis. We will also analyze the 24 36 and 48 week endpoints compared to baseline this way. Trajectory changes will be first analyzed by graphs relating activity (in minutes) at each data collection time. We will also analyzed slopes of activity, it possible. Responder non-responder analyses will be performed using logistic analysis with demographics and baseline disease characteristics as potential predictor variables.

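### The valid-day rule counts 12 worn hours per 24-hour day without excluding night wear, so it does not guarantee the 75% coverage used to justify it

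*Combined protocol and SAP*

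**What the plan says.** The rule and its justification stand close together in the Protocol synopsis, item 6 (Comments).

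- The rule: "Twelve hours per 24 hour day of activity assessment will be considered a day's measurement".
- The expected wear pattern: "Although we will ask patients to wear the devices day and night, we anticipate many will not wear them at night because of inconvenience".
- The justification drawn from it: "Therefore, a requirement of 12 of a potential 16 hours (75% wear-time) appears reasonable".
- How wear is established: "The DynaPort device has an algorithm that determines wear time".

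The activity-measurement paragraph under Sample size estimates gives the minimum per assessment, "Activity will be measured for 7 consecutive days, 3 days (12 hours per day) minimum", and the instruction to patients, "Patients will be asked to wear the devices 24 hours per day, if possible".

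Night wear also has a use of its own. Sleep efficiency and awakenings from the same device are candidate predictors of baseline activity, and the measurement table lists them at all five visits.

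Under Data analysis, "The primary variable to be assessed will be changes in daily walking activity (in minutes) from baseline to week 12". Day of week and season are named as covariates. Wear time is not named, although the section allows covariates to be added.

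**The concern.** One 12-hour threshold has two denominators: 24 hours in the rule and 16 hours in the reasoning behind it. They agree only for a patient who takes the device off at night. For a patient who keeps it on overnight, night hours can make up most of the 12, and the documents do not say that those hours are left out of the count.

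Walking minutes accrue while the patient is awake. A day that qualifies largely on sleep enters the visit mean as a day of little walking, although most of the waking day was not observed. If such days are equally common at baseline and week 12, they shrink the measured change. If they are not, they bias it in whichever direction the imbalance runs, and this study has no control group against which a shift in wear pattern would cancel.

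**Working it through.** **Inputs from the documents.** 12-hour threshold, 24-hour day, 16-hour denominator and 75% (Protocol synopsis, item 6). Seven days of recording with a minimum of three (Sample size estimates). Walking time of 36 min/day, the baseline of the treated group in the cited lung-transplant exercise trial, and planning effects of 10 and 8 min (Sample size estimates).

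**Assumptions.** Sleep of 8 hours, implied by 24 − 16 = 8 but not stated, with a range of 6 to 10 hours. Walking spread evenly over waking hours. All other days in the assessment fully captured.

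**1. The plan's own figure.** 12/16 = 75%. It reproduces, with no night hours in the count.

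**2. The floor when night hours count.** With s hours of sleep and h of them worn, a day that just passes has 12 − h waking hours worn, a fraction (12 − h)/(24 − s) of waking time.

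For s = 8:
- h = 0: 12/16 = 75%
- h = 4: 8/16 = 50%
- h = 8: 4/16 = 25%, with 8/12 = 67% of worn time asleep

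With the whole night worn and other sleep lengths:
- s = 6: 6/18 = 33%
- s = 7: 5/17 = 29%
- s = 9: 3/15 = 20%
- s = 10: 2/14 = 14%

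**3. How such a day could arise.** One route is overnight wear followed by a long daytime removal. Another is a partial first or last day, if days are calendar days (an assumption, since the documents do not define the day boundary). A device worn overnight and removed at noon on the last day has 12 hours from midnight. These hold 4 waking hours if sleep runs from midnight to 08:00, or 5 if it runs from 23:00 to 07:00, giving 25% or 5/16 = 31%.

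**4. Effect on one patient's visit mean.** The rate is 36/16 = 2.25 min per waking hour. A 25% day records 4 × 2.25 = 9 min, a 75% day 12 × 2.25 = 27 min, a full day 36 min.

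| One such day among | Loss against a day at the 75% floor | Loss against a full day |
|---|---|---|
| 3 days | (27 − 9)/3 = 6 min | (36 − 9)/3 = 9 min |
| 7 days | (27 − 9)/7 = 2.6 min | (36 − 9)/7 = 3.9 min |

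The first column is the fairer comparison, because the plan already accepts a 75% day.

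**5. From patient to group.** Suppose a true gain of 10 min, with one 25% day at each visit in an affected patient. The measured gain is 10 × (6 + 0.25)/7 = 8.9 min with 7 days, or 10 × (2 + 0.25)/3 = 7.5 min with 3. The group mean loses 1.1 or 2.5 min times the proportion of patients affected. If half were affected (illustrative), that is about 0.5 or 1.25 min.

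If the proportion affected differed by 20 percentage points between visits (illustrative) and there were no true change, the artefact would be 3.9 × 0.2 = 0.8 min with 7 days, or 9 × 0.2 = 1.8 min with 3, measured against full days. Its sign depends on which visit has more such days.

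**The case against.** The strongest reply is that the plan already means waking hours. The 12-of-16 sentence follows the rule closely and calls itself a requirement, so the two can be read together as asking for 12 of the hours outside the night. That may well be the intent, and the claim that sleep counts is an inference from silence. What remains is that the operative sentence says 24 hours, nothing says sleep is excluded, and the documents do not say that the device's wear-time algorithm separates sleep from waking for this purpose. Six sites or a programmer could apply the literal wording.

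Other parts of the defence stand. For patients who remove the device at night, the pattern the plan expects of many, the rule does deliver 75%. The plan speaks of wear time and never of waking hours; the waking reading is implied. The 36 min/day comes from lung-transplant patients. The study describes itself as mainly hypothesis-generating, and wear time could be added as a covariate.

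Three stronger conclusions are tempting and not supported:

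- A reader might infer that the plan expects night wear to fall off after the first assessment, which would depress baseline and create a false gain. The plan expects many patients not to wear the device at night. It says nothing about a change between visits.
- A reader might infer that patients who follow the wear instruction get the worse data. A patient who wears the device for the full 24 hours has complete waking data. The problem needs night wear together with daytime removal or a partial day.
- A reader might set the 6 or 9 min against the 8 and 10 min planning effects and conclude that the effect could be wiped out. The former apply to one affected patient at one visit; the latter are group means.

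**Conclusion.** The point holds as a defect in the stated rule. As written, the valid-day definition does not guarantee the 75% coverage offered in its support. For a patient wearing the device overnight, the floor is about 25% of waking hours with 8 hours of sleep, and 33% to 14% with 6 to 10 hours.

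The minute losses rest on the borrowed baseline value and on even spread of walking through the day. The documents give neither the frequency of such days nor a definition of the day boundary, so the effect on the primary result cannot be quantified. It is probably small and its direction is not known in advance: equal frequency at the two visits attenuates the change, and unequal frequency biases it either way. The stated sample sizes are unaffected. The correction is worth making because it is specific and cheap and brings the rule into line with its own rationale.

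**What to change.** In the activity-measurement paragraph under Sample size estimates and in the Protocol synopsis, item 6, state that:

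- the 12 hours of wear must fall within the 16 hours outside the night, and night wear does not count towards them;
- those 16 hours are defined the same way at every visit, either as a fixed daytime window (shifted by one stated rule for patients with unusual sleep times) or as wear the device classes as non-sleep;
- partial first and last days that fail are dropped;
- the three-valid-day minimum stays.

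The floor is then 12/16 = 75% whatever the night wear. The request for 24-hour wear can stay, since the sleep variables need it.

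The cost is a wording change and a filter on the wear record. The filter assumes that the device output gives wear by clock time or sleep state, which should be confirmed because the documents say only that wear time is determined. A few days, and occasionally a whole assessment, will fail the minimum and fall under the plan's missing-data rule, which carries the last observation forward. Applied at week 12, that would put the baseline value in place of the primary measurement, so the number of assessments lost this way should be reported.

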as the primary outcome, rather than vector magnitude units (VMU) or estimated steps per day. The DynaPort device was rated favorably by PROactive COPD (<http://www.proactivecopd.com>) which tested accelerometers. Additionally, there is too much variability in VMU, and estimated steps per day in slow moving COPD patients are inaccurate. Minutes per day of walking activity appears to be a more useful outcome. Walking activity from the DynaPort has been demonstrated to be very responsive to exercise training in lung transplant patients. (8) Finally, more information is needed to determine the factors that influence the translation of exercise capacity gains realized in the rehabilitation center into increased physical activity in the home and community settings. One editorial commented that it takes 3 months to train the muscles and 6 months to train the brain.(9) We will explore potential factors influencing this important outcome, including baseline activity levels, demographic variables, changes in exercise capacity, psychological variables, and self-efficacy scores. Finally, we will evaluate the rate of change (trajectory) in physical activity over approximately six months after the pulmonary rehabilitation intervention. There are limited data suggesting it takes time for the translation of increased exercise capacity into increased physical activity to occur. (10) If our study corroborates these findings, it would potentially influence our therapeutic approach to the physically inactive COPD patient.

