### **Design:**

This will be predominately a hypothesis-generating study. Its general design is that of a longitudinal study (without a control group) evaluating directly-measured physical activity in COPD patients who had participated in pulmonary rehabilitation. Activity measurements will be at baseline (before exercise training is started), and at approximately 12, 24, 36, and 48 weeks (+/- 3 weeks at each time period) following pulmonary rehabilitation. There will be no direct change, per protocol, in the patient's pharmacological treatment for COPD (controller or rescue inhaler medication) or other medical problems; this treatment will be directed by the patient's health care provider.

Three distinct types of analysis will be performed:

1. Evaluation of changes in physical activity before and after pulmonary rehabilitation

2. Predictors of baseline physical activity
3. Predictors of *change* in physical activity following pulmonary rehabilitation.

This will be an intent-to-treat analysis, providing patients complete 50% or more of the pulmonary rehabilitation sessions. Those dropping out with less than 50% attendance will be dropped from the study.

Dealing with Exacerbations: It is anticipated that patients will have COPD exacerbations over the course of the study. Since exacerbations themselves affect physical activity, activity testing will be postponed for 2 weeks following the clinical end of the exacerbation. We have determined that physical activity returns to close to baseline by two weeks after the exacerbation (Ehsan et al, A Longitudinal Study Evaluating the Effect of Exacerbations on Physical Activity in Patients with Chronic Obstructive Pulmonary Disease. Annals of American Thoracic Society 2013; 10(6):559-64). If two exacerbations occur within the same time block, testing for that period will not be performed, and the last observation will be carried forward. If a patient is hospitalized for an exacerbation, that patient will be dropped from the study.

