Comment: We will not be altering the pharmacological management of the patient; this study will focus only on the pulmonary rehabilitation component and specifically how it affects physical activity. It is currently almost impossible to carry out a randomized, controlled trial of pulmonary rehabilitation, since the intervention is considered a gold standard of therapy. The within-group analysis without a control group would be feasible and would not raise ethical issues. While this approach (without a control group) limits the strength of conclusions, the primary intent of this analysis is to explore the rate of change in physical activity with pulmonary rehabilitation (realizing that it probably takes longer to improve than exercise capacity) and predictors of response to the intervention.

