**Hypotheses to be tested:**

Changes in activity following pulmonary rehabilitation

1. Compared with baseline, COPD patients participating in outpatient pulmonary rehabilitation will show an increase in directly-measured physical activity

- (minutes per day of walking activity from the DynaPort) at the  $12 \pm 3$  week assessment. (primary hypothesis)
2. Compared with baseline, COPD patients participating in outpatient pulmonary rehabilitation will show increases in upright activity, activity intensity, steps per day, minutes with METs  $> 2$  (from the DynaPort) after  $24 \pm 3$ ,  $36 \pm 3$  and  $48 \pm 3$  weeks
  3. Exploratory: We will analyze the trajectory of physical activity over the 48 weeks after initiating pulmonary rehabilitation.

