#### Predictors of *change* in physical activity

5. Exploratory: We will be able to identify responders versus non-responders with respect to: 1) the change in activity at 12 weeks, and 2) the trajectory (over 48 weeks) in these activity measurements; this will include the slopes of change in physical activity. We will then relate baseline variables to responder status. We cannot a priori determine a threshold for physical activity responder status; this will have to be done a posteriori when data are available. We anticipate from the post-lung transplant study the responder threshold will be an increase in 10 minutes walking time per day. Predictor variables are listed above.

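### Last observation carried forward is the only imputation rule for missing activity recordings; it mutes change after week 12 in either direction, with no alternative or sensitivity analysis planned

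*Combined protocol and SAP*

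**What the plan says.** Protocol synopsis, item 6 (Comments), covers any recording missing during the 48 weeks, for example through technical problems or repeated exacerbations: "we will carry the last observation forward into that missing spot". Design, under Dealing with Exacerbations, repeats the rule for one case: "If two exacerbations occur within the same time block, testing for that period will not be performed, and the last observation will be carried forward".

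Data analysis compares weeks 12, 24, 36 and 48 with baseline by repeated measures ANOVA, with season and day of week as covariates, and plans slopes if feasible. It does not mention carried values, another method for gaps, or a sensitivity analysis.

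The uses of the later visits are stated elsewhere:
- Design, Comment: "the primary intent of this analysis is to explore the rate of change in physical activity with pulmonary rehabilitation", together with predictors of response.
- Hypotheses to be tested: "Exploratory: We will analyze the trajectory of physical activity over the 48 weeks after initiating pulmonary rehabilitation".
- Predictors of change, on classifying responders by trajectory: "this will include the slopes of change in physical activity".

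For week 12, Sample size estimates says: "Our goal will be to recruit 40 patients with evaluable data at 12 weeks". The term evaluable is not defined.

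**The concern.** Carrying a value forward assumes that nothing changed across the gap. The study exists because something may change. Background and rationale says: "There are limited data suggesting it takes time for the translation of increased exercise capacity into increased physical activity to occur". A late gain is therefore the signal of interest, and loss of benefit after rehabilitation is the obvious competing outcome. The rule pulls both towards no change.

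A carried value is typically about 12 weeks old, and older after consecutive gaps. It also has no recording dates of its own, and the plan does not say which season it takes in the covariate adjustment.

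The individual slopes are most exposed, because they feed responder status, which is then related to baseline variables. If gaps cluster in patients who exacerbate often, predictors of response could partly reflect who had gaps.

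**Working it through.** **Inputs.** From Sample size estimates: SD of change 20 min, 40 evaluable patients, and a 10-minute gain as a planning value. Assumed, because the plan gives none: two-sided alpha 0.05; a missing rate p of 10, 20 or 30% at each of weeks 24, 36 and 48, independent of activity; week 12 always measured; and true gains over baseline that run linearly from +10 at week 12 to either 0 (fall) or +15 (rise) at week 48.

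**1. The plan's own figures.** A paired t-test (noncentral t, SD 20, power 0.80) gives n = 12, 34 and 52 for 18, 10 and 8 min, as stated. Forty evaluable with 20% loss gives 40/0.8 = 50, as stated. The standard error of a mean change is 20/√40 = 3.16 min.

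**2. Visit means.** Expected carried-forward mean: L₁₂ = μ₁₂, then Lₖ = (1−p)μₖ + pLₖ₋₁.

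| p | Fall: weeks 12, 24, 36, 48 | Rise: week 48 |
|---|---|---|
| true | 10, 6.67, 3.33, 0 | 15 |
| 10% | 10, 7.00, 3.70, 0.37 | 14.82 |
| 20% | 10, 7.33, 4.13, 0.83 | 14.59 |
| 30% | 10, 7.67, 4.63, 1.39 | 14.30 |

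A flat course gives no bias.

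**3. Group slope, weeks 12-48.** Least-squares weights are (−18, −6, 6, 18)/720. The true fall is −200/720 = −0.278 min/week. With carrying forward it becomes −0.268, −0.256 or −0.241, so 3.4, 7.8 or 13.4% is hidden. The rise loses the same percentages.

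**4. Group slope with baseline included.** The plan does not fix the window. With weights (−24, −12, 0, 12, 24)/1440, the rise has a true slope of 400/1440 = 0.278 and loses 2, 4 or 6%. The fall has a true slope of only −80/1440 = −0.056 and loses 17, 37 or 61% of it.

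**5. One patient's slope, weeks 12-48, linear fall.**
- Missing week 48: −140/720 = −0.194, a 30% loss.
- Missing weeks 36 and 48: −60/720 = −0.083, a 70% loss.
- Missing all three: 0, a 100% loss.
- Missing week 24 alone: −220/720 = −0.306, 10% too steep.

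With baseline included, the first three losses for the rise are 10, 25 and 40%. The share of patients with at least one filled value is 1−(1−p)³ = 27, 49 or 66%.

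**6. Error term.** Simulation used n = 40, five visits, equal correlation 0.5 and change SD 20, so the true residual mean square is 400/2 = 200. If one ANOVA error term covers all visits, carrying forward shrinks it to about 194, 186 or 178. A weeks 12-48 slope test then rejects a truly flat course about 6, 6.7 or 7.4% of the time. Coverage of the 95% interval under the fall is about 94, 92 or 90%. With one slope per patient and a t-test, rejection stays near 5% and coverage is about 95, 94 or 93%.

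**7. Week 12.** If only baseline and week 12 enter the model, gaps at later visits leave the test at 5%. If all visits share the error term, it is about 5.3, 5.8 or 6.4%. If m of 40 week-12 values were themselves filled from baseline and those patients truly gained 10 min, the mean falls by 10m/40: 0.25, 0.5 or 1.0 min for m = 1, 2 or 4. Power is 0.86, 0.85 or 0.83, within 0.01 of using measured patients only. Each filled patient is a non-responder at any threshold above zero.

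**8. Gaps after two exacerbations.** If a share q is untested and truly d min below the last value, that visit's mean is overstated by q×d. With q of 5-20% and d of 0-10 min (both assumed), this is 0 to 2.0 min.

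**The case against.** The case for leaving the rule alone is substantial. The study is uncontrolled and mainly hypothesis-generating, and trajectory and responder analyses are labelled exploratory. The shifts in visit means are below one standard error, and a flat course is unbiased. Other rules reduce gaps: testing is postponed after an exacerbation, off-window recordings are accepted, and some patients are dropped. The slope window, the slope test and the pooled error term used above are not specified in the plan. All of this stands, and it limits severity and makes the percentages illustrative. It does not make the rule neutral for the quantity that the study mainly wants to explore.

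For gaps after exacerbations, the sponsor can point to its own finding: "We have determined that physical activity returns to close to baseline by two weeks after the exacerbation". If that held after two events in one block, the bias in step 8 would be nil. The sentence concerns a single exacerbation and does not establish it.

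A reader might also infer more than the documents support:
- **That the primary result is compromised.** The target of evaluable data at 12 weeks probably means measured data, and step 7 shows little effect either way. The gap is one of wording: the carry-forward sentence exempts no visit.
- **That the rule favours rehabilitation.** It flatters a fading benefit and penalises a growing one, so no single direction follows.
- **That type I error is inflated.** This depends on pooling the error term across visits.
- **That the plan has no other provision for missing data.** Carrying forward is the only imputation rule, not the only rule.
- **That the rule on blocks with two exacerbations conflicts with accepting off-protocol dates.** The latter mainly concerns patients who cannot attend.

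That filled values are treated as measured is itself inferred from the silence of Data analysis.

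**Conclusion.** The point holds as a modest should-fix. The plan's only imputation rule assumes no change across a gap in a study of change over time, and nothing in the plan checks that assumption. At assumed missing rates of 10-30% the group-level effect is small: up to about 1.4 min at week 48 and 3-13% of the weeks 12-48 slope. It is larger relative to a small slope when baseline is included and benefit fades. The effect on individual slopes, and so on slope-based responder status, can be large for patients with late or repeated gaps. The primary week-12 comparison is not materially affected, and the week-12 request is a clarification. These sizes rest on assumed missing rates, linear courses and gaps unrelated to activity. The plan does not say whether later visits of patients dropped after a hospitalised exacerbation are filled, so these are not included.

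**What to change.** 1. Delete the carry-forward clause in Design (Dealing with Exacerbations) and the carry-forward sentence in Protocol synopsis, item 6.
2. In Data analysis, specify a likelihood-based mixed model for repeated measures on all measured recordings, without imputation: visit categorical and a stated covariance structure. Week 12 minus baseline is the primary contrast, and weeks 24, 36 and 48 come from the same model. Use actual recording times for slopes.
3. State that week-12 change and responder status need a measured baseline and a measured week-12 recording, each meeting the plan's own minimum of three days of 12 hours. Define evaluable in Sample size estimates in the same words.
4. Report the number of missing recordings and the reasons, by visit.
5. Add one sensitivity analysis that shifts the values missing after two exacerbations over a range labelled as an assumption, for example 0 to 10 min/day lower. Carrying forward may stay only as a further sensitivity analysis.

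The cost is analysis wording and one extra analysis in SAS, which is already planned. The sample size does not change, and no change to testing or clinical rules is proposed. There are two downsides. The model relies on missing at random, which is why item 5 is needed. The week-48 standard error is also larger: about 3.4 min at 20% missing, against √(2×186/40) = 3.05 reported with carrying forward. The latter is itself too small, because it comes from the shrunken error term.
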